1. PROTOCOL SUMMARY

PRODUCT NAME/NUMBER: TLC599 (Lipid-based Dexamethasone Sodium Phosphate Sustained Release Formulation)
PROTOCOL NUMBER: TLC599A3005
DEVELOPMENT PHASE: Phase 3
PROTOCOL TITLE: A Phase 3, Randomized, Double-blind, Placebo- and Active-controlled Study to Evaluate the Efficacy and Safety of TLC599 in Patients with Osteoarthritis of the Knee
INDICATION: Osteoarthritis of the knee
PLANNED STUDY SITES: Approximately 45 to 50 study sites in the United States and Australia
OBJECTIVES
Primary Objective:

To evaluate the efficacy of a single intra-articular (IA) dose of TLC599 in patients with osteoarthritis (OA) of the knee
Secondary Objectives:

To evaluate the efficacy of repeat doses of TLC599 in patients with OA of the kneeTo evaluate the safety of single and repeat IA doses of TLC599 in patients with OA of the knee
RATIONALE
Osteoarthritis is a common degenerative joint disorder of the articular cartilage associated with hypertrophic bone changes. Treatment for OA primarily involves a non-pharmacological combination of exercise and lifestyle modification, pharmacological treatment, supplementation with glucosamine or chondroitin sulphate, and surgical joint replacement. Among pharmacological treatments, corticosteroids have both anti-inflammatory and anti-angiogenic properties, and they are routinely given via inject IA injection for the treatment of chronic knee joint diseases to relieve pain, reduce inflammation, and improve mobility.
IA corticosteroid injection is a commonly used treatment with an excellent safety profile. A limitation of IA injection with corticosteroids is the modest duration of treatment effect, which often lasts for only 2 to 4 weeks. Repeat injections are possible in the same joint, but there are limited data on the safety and duration of the effectiveness of this procedure. Thus, there is a pressing need for a more sustained duration of an IA corticosteroid injection.
Taiwan Liposome Company (TLC) is developing TLC599, a sustained release liposomal formulation of dexamethasone sodium phosphate (DSP) for the treatment of OA. DSP, an injectable form of dexamethasone, is formulated with lipid excipients to allow a sustained release of DSP to maintain therapeutic concentrations of dexamethasone in the joint space for an extended period of time. The formulation of TLC599 is specifically designed to provide both immediate-release DSP and long-acting liposomal form of DSP, providing both short-term and sustained pain and symptom relief for up to 6 months in patients with knee OA pain. To date, TLC has completed 2 studies to evaluate the safety and efficacy of a single-dose IA injection of TLC599 in patients with knee OA. Based on data from both trials, TLC599 with 12 mg DSP demonstrated a rapid onset of OA pain and symptom relief, with sustained therapeutic benefit up to 6 months with a single IA injection.
METHODOLOGY
Study Design:

This is a Phase 3 randomized, double-blind, placebo- and active comparator-controlled pivotal study.Efficacy and safety of 2 doses of TLC599 will be evaluated in comparison with Placebo and DSP through Week 52.Approximately 500 adult patients with moderate to severe pain due to OA of the knee will be randomized in a 2:1:1 ratio to receive TLC599 12 mg (Group A), DSP 4 mg (Group B), or Placebo (normal saline) (Group C) via IA injection into the designated index knee at Baseline (Injection 1).At Week 24, patients will receive blinded Injection 2 per their randomly assigned dosing regimen (Group A, B, or C) via IA injection into the index knee. Patients who received TLC599 12 mg (Group A) or DSP (Group B) for Injection 1 will receive blinded TLC599 12 mg for Injection 2 and those who received Placebo for Injection 1 (Group C) will receive Placebo for Injection 2.

- All patients will be followed for a total of 52 weeks, regardless of whether or not they receive Injection 2. Patients who do not receive Injection 2 at the Week 24 Visit will be encouraged to continue in the study through the entire 52 weeks of follow-up.
- The study design and visit schedule are illustrated in the following figure:

Abbreviations: BL = Baseline (Day 1); DSP = dexamethasone sodium phosphate; Rand = Randomization; SCR = Screening; W = Week.

Study Procedures:

- Patients will be screened for eligibility at Visit 1 (Screening); procedures will include, but is not limited to, medical history and concomitant medication review, knee pain assessments, knee radiographs, physical examination, and clinical laboratory assessments. Initial eligibility for pain in each knee will be assessed using a patient-reported numeric rating scale (NRS) (rating of average pain over the previous 24 hours).
- Patients will be trained on the use of diaries, accurate pain reporting, and appropriate expectations for a clinical trial.
- During the screening period, patients will complete daily diaries including assessments of pain in each knee by NRS as well as rescue medication use. Every evening, patients must score their average pain in each knee by NRS over the previous 24 hours. The diary must be completed for at least 5 of the last 7 days of the screening period before returning to the study site for Visit 2 (Baseline/Day 1).
- At Visit 2 (Baseline/Day 1), after baseline assessments, eligibility will be confirmed and the index knee will be determined, and eligible patients will be randomized in a 2:1:1 ratio to receive TLC599 12 mg (Group A), DSP 4 mg (Group B), or Placebo (Group C) via IA injection into the index knee (Injection 1).
- Patients will return to the study site at Week 1, Week 2, Week 4, and every 4 weeks through Week 24 to complete efficacy and safety assessments as applicable.
- At Week 24, patients (see Criteria for Injection 2 [Week 24]) will receive blinded Injection 2 via IA injection into the index knee according to their randomly assigned dosing regimen: TLC599 12 mg (Groups A and B) or Placebo (Group C).
- Patients will continue to return to the study site every 4 weeks through Week 52 to complete efficacy and safety assessments as applicable.
- Patients who receive Injection 2 at Week 24 will also return to the study site at 1 week (Week 25) and 2 weeks (Week 26) after Injection 2.
- Patients who do not receive Injection 2 will continue to be followed through Week 52. Patients who do not complete the study through Week 52 will complete early termination procedures.

VISIT STRUCTURE: There will be up to 19 study visits, including Screening (Visit 1), Baseline (Day 1/Visit 2), Week 1 (Visit 3), Week 2 (Visit 4), and 6 visits occurring every 4 weeks from Week 4 (Visit 5) through Week 24 (Visit 10), Week 25 (Visit 11), Week 26 (Visit 12), and every 4 weeks from Week 28 (Visit 13) through Week 52 (Visit 19). Week 25 (Visit 11) and Week 26 (Visit 12) will only be required for patients who receive Injection 2 at Week 24 (Visit 10).

STUDY DURATION: Duration of patient participation will be up to 56 weeks, including a Screening period of up to 4 weeks before randomization, Injection 1 Period of 24 weeks and Injection 2 Period of 28 weeks.

STUDY POPULATION

This study will randomize approximately 500 patients, according to the following inclusion and exclusion criteria:

Inclusion Criteria:

1. Male or female ≥ 40 years of age, inclusive.
2. Body mass index $\leq 40 \text{ kg/m}^2$.
3. Has symptoms associated with OA of the index knee for at least 6 months before Screening.
4. Documented diagnosis of OA in the index knee based on American College of Rheumatology Criteria for Classification of Idiopathic OA of the knee (clinical and radiological including standing fixed-flexion posterior-anterior X-ray of the knee).
5. OA with Kellgren-Lawrence Grade 2 to 3 severity in the index knee based on the grade per X-ray assessed by a central radiologist reader at Screening.
6. Initial patient-reported pain with NRS score ≥ 4 (on a 0-10 scale) in at least 1 knee (index knee) at Screening (rating of average pain over the previous 24 hours).
7. Patient-reported pain with average daily NRS score of 5.0 to 9.0 (inclusive) in the index knee, AND with non-index knee pain score of ≤ 4.0 , based on diaries completed daily for at least 5 of the last 7 days of the screening period before randomization.
8. Patient-reported WOMAC Pain sub-scale (hereafter referred to as WOMAC Pain) score ≥ 6 (combined score on a 0-20 scale) in the index knee before dosing at Baseline.
9. a. IF FEMALE, must meet all of the following:
 - Not breast feeding;
 - Not planning to become pregnant during the study;
 - If of childbearing potential (defined as non-post-hysterectomy or non-post-menopausal [amenorrheic for at least 2 years]), must have a negative pregnancy test result (human chorionic gonadotropin, beta subunit [β -hCG]) at Screening and Baseline, and must commit to the use of an acceptable and effective form of birth control for the duration of the study and until at least 6 months after the last dose of study drug.
- b. IF MALE, must be surgically sterile (biologically or surgically) or commit to the use of a reliable method of birth control (must agree to use double-barrier contraception in the event of sexual activity), or be practicing abstinence for the duration of the study and until at least 6 months after the last dose of study drug.

10. Is able to read, understand, and sign the informed consent form (ICF), communicate with the investigator, and understand and comply with protocol requirements.

Exclusion Criteria:

1. Use of any of the following medications within the specified period:
 - a. IA corticosteroid in any joint within 3 months before Screening, or triamcinolone acetate extended-release injectable suspension (Zilretta[®]) within 6 months before Screening
 - b. IA hyaluronic acid in any knee joint within 6 months before Screening
 - c. Systemic corticosteroids within 4 months before Screening or chronic use within 1 year before Screening
 - d. NSAIDs (except topical use on regions other than the index knee) within 14 days before the Baseline visit
 - e. Platelet-rich plasma or other prolotherapy within 6 months before Screening
 - f. Chronic opioid use (use exceeding 4 days per week) within the last 30 days before Screening.
 - g. Any chemotherapeutic or systemic immunosuppressant agents for inflammatory diseases within 6 months before Screening
 - h. Anti-coagulants, including warfarin, heparin, low molecular weight heparin, or dabigatran within 1 week of Screening and the Baseline visit. Low-dose acetylsalicylic acid or other anti-platelet medications are allowed
 - i. Live attenuated vaccine within 3 months before Screening
 - j. Any investigational therapy within 4 weeks or within 5 half-lives before Screening, whichever is longer
2. Patient who is not ambulatory.
3. Any surgery or arthroscopy in the index knee within 12 months before Screening.

4. Unstable index knee joint as determined by the investigator based on physical examination (with or without buckling or giving way) because of an acute injury (defined as injury within 6 months of Screening, e.g., anterior cruciate ligament injury or tear).
5. History of infective arthritis in the index knee.
6. Suspected/concurrent infection in either knee at Screening or Baseline before study drug administration.
7. Any skin lesion/breakdown at the anticipated injection site or any condition that impairs penetration of the index knee joint space.
8. Documented gout attack in index knee within 6 months before Screening or presence of tophus in index knee.
9. Patient with any amputation in any lower limb.
10. Documented history and confirmed autoimmune disease including but not limited to, reactive arthritis, systemic lupus erythematosus, Sjögren's syndrome, systemic sclerosis, inflammatory myositis, mixed connective tissue disease, palindromic rheumatism, reactive arthritis, rheumatoid arthritis, psoriatic arthritis, ankylosing spondylitis, Behcet's disease, arthritis associated with inflammatory bowel disease, sarcoidosis, vasculitis, cryoglobulinemia, or amyloidosis.
11. Any condition that could possibly confound the patient's assessment of index knee pain per the investigator's judgment (i.e., ipsilateral hip OA, radicular low back pain, and hip pain referred to the index knee).
12. Substance abuse disorder, or positive urine drug test for illegal drug substances or non-prescribed controlled substances including amphetamines, barbiturates, benzodiazepines, cocaine, opiates, phencyclidine, and tetrahydrocannabinol; or positive alcohol breath test.
13. History of primary or secondary adrenal insufficiency.

16. History of bleeding disorders.
17. History of acquired or congenital immunodeficiency diseases, or positive test results for human immunodeficiency virus (HIV), hepatitis B virus (HBV), or hepatitis C virus (HCV) current infection at Screening.
18. Any active infection requiring treatment with antibiotics.
19. History of treated malignancy which is disease free for ≤ 5 years before Screening, except basal cell carcinoma of skin or carcinoma in situ of the uterine cervix.
20. Stroke or myocardial infarction within 12 months before Screening.
21. Uncontrolled and unstable concurrent medical or psychiatric illness, including but not limited to, poorly controlled diabetes, poorly controlled hypertension, dementia, schizophrenia, or bipolar disorder that will jeopardize the safety of the patient, interfere with the objectives of the protocol, or affect the patient compliance with study requirements, as determined by the investigator.
22. Abnormalities of the following laboratory parameters at Screening:
 - a. HbA1c >9.0%
 - b. platelet count <80,000/ μ L
 - c. hemoglobin <8.0 g/dL
 - d. total white blood cell count <4000/ μ L
 - e. serum bilirubin/alanine aminotransferase/ aspartate aminotransferase >2 times upper limit of normal (ULN) for the laboratory reference ranges
 - f. serum creatinine level >1.5X ULN
 - g. prothrombin time/International Normalized Ratio > ULN for the laboratory reference range
23. Known allergy or hypersensitivity to the study drugs or their components.
24. Is an immediate family member (spouse, parent, child, or sibling; biological or legally adopted) of personnel directly affiliated with the study at the clinical study site.
25. Employed by sponsor (i.e., is an employee, temporary contract worker, or designee responsible for the conduct of the study).

Criteria for Injection 2 (Week 24):

Patients will not continue with Injection 2 if any of the following criteria are met:

2. Occurrence of adrenal insufficiency through Week 24.
3. If female and of childbearing potential, have a positive urine pregnancy test result at Week 24.
4. Positive urine drug or alcohol test result at Week 24. (Drug use allowed with prescription.)

STUDY DRUGS

Study drug will be administered in a blinded manner via IA injection into the index knee.

- **Study Drug (TLC599):**
 - Dexamethasone sodium phosphate (DSP) 12 mg with 100 mM phospholipid (PL) (1 mL)
- **Reference Drug (DSP):**
 - DSP 4 mg (1 mL)
- **Placebo:**
 - Normal saline (1 mL)

Patients will be randomly assigned to one of the following treatment groups in a 2:1:1 ratio.

Group	Injection 1 (Day 1)	Injection 2 (Week 24)
A	TLC599	TLC599
B	DSP	TLC599
C	Placebo	Placebo

Rescue Medication:

- Total acetaminophen use up to 3 g/day (not allowed within 24 hours before study visits)

ASSESSMENTS

Efficacy Assessments:

- Western Ontario & McMaster Universities Osteoarthritis Index (WOMAC, Version 3.1)
 - WOMAC comprises 24 questions, each on a 0-4 Likert scale (total score on a 0-96 scale) with assessment based on the previous 24 hours
 - Sub-scale scores of Pain (5 items, total sub-scale score on a 0-20 scale), Stiffness (2 items, total sub-scale score on a 0-8 scale), and Physical Function (17 items, total sub-scale score on a 0-68 scale) are added together to determine the WOMAC Composite score
 - Composite and sub-scale scores of WOMAC will be normalized to a scale of 0-4 for analysis.
- Patient Global Impression of Change (PGIC)
 - PGIC is a single-item question that measures change in patients' overall improvement rated on a 7-point scale including "very much improved," "much improved," "minimally improved," "no change," "minimally worse," "much worse," or "very much worse"
- 
- Numeric rating scale (NRS) for average pain, as recorded on a daily patient diary
 - 0-10 scale, with 0 representing "no pain" and 10 as "the worst possible pain"
 - Every evening patients will assess their average pain intensity for the previous 24 hours
- Use of rescue medication for index knee pain: acetaminophen as recorded in a daily patient diary

Safety Assessments:

- Patient safety will be evaluated by physical examination, vital signs assessments (heart rate, respiratory rate, sitting blood pressure, and temperature), clinical laboratory assessments (hematology, chemistry, urinalysis), HbA1c, morning serum cortisol,  12-lead electrocardiogram (ECG), knee radiographs, concomitant medications/therapies, adverse events (AEs), and signs and symptoms of adrenal insufficiency.

ENDPOINTS

The primary efficacy endpoint is:

1. Change from Baseline in WOMAC Pain at Week 12 (Group A vs. Group C)

The secondary efficacy endpoints are:

1. Change from Baseline in WOMAC Pain at Week 16 (Group A vs. Group C)
2. Change from Baseline in WOMAC Pain at Week 20 (Group A vs. Group C)
3. Change from Baseline in WOMAC Pain at Week 24 (Group A vs. Group C)
4. Change from Baseline in WOMAC Pain at Week 36 (Group A vs. Group C)
5. Change from Baseline in WOMAC Function at Week 12 (Group A vs. Group C)
6. Patient Global Impression of Change (PGIC) at Week 12 (Group A vs. Group C)
7. Total rescue acetaminophen consumption through Week 12 (Group A vs. Group C)
8. Durable responder with $\geq 30\%$ decrease in WOMAC Pain from Baseline for Weeks 4 through 12 (Group A vs. Group C)
9. Change from Baseline in WOMAC Function at Week 36 (Group A vs. Group C)
10. PGIC at Week 36 (Group A vs. Group C)
11. Change from Baseline in WOMAC Pain at Week 12 (Group A vs. Group B)
12. Change from Baseline in WOMAC Pain at Week 52 (Group A vs. Group C)

STATISTICAL METHODS

General Statistical Considerations:

All efficacy and safety data will be listed and descriptively summarized by injection (Injection 1 or Injection 2) and treatment group (Group A, B, or C). Continuous variable summaries will include the number of patients, mean, standard deviation (SD), first quartile, median, third quartile, minimum, and maximum. Categorical variables will include the frequency and percentage of patients in each category. All statistical assessments will be 2-sided 0.05 significance level.

Database lock and unblinding will occur after the last patient in the study has completed the study.

Analysis Populations:

- **Safety Population (SAF):** The Safety Population includes all patients who receive any dose of study drug; the population will be determined for each study period. The SAF population will be the primary population for safety evaluation.
- **Full Analysis Set (FAS):** The FAS includes all randomized patients who receive Injection 1. The FAS population will be the primary population for efficacy analysis, as well as for descriptive summaries other than safety (demographic and baseline, disposition, protocol deviations, medical history, etc.).
- **Per Protocol Population (PP):** The PP Population includes all patients who receive 2 doses of study drug, have primary efficacy evaluation at Weeks 12, 24, and 36, and do not have important protocol deviations affecting primary efficacy evaluation.
- **Modified Per Protocol (mPP):** The mPP Population includes all patients who receive the first dose of study drug, have primary efficacy evaluation at Weeks 12 and 24, and do not have important protocol deviations affecting primary efficacy evaluation.

Efficacy Analysis:

Analysis of Primary and Key Secondary Endpoints:

Efficacy variables will be descriptively summarized by treatment group and by injection period within each group, based on the FAS population, unless otherwise specified. For all the continuous variables, the normalized numbers will be used for analysis, where applicable, unless otherwise specified.

The overall type I error rate will be controlled for primary and key secondary endpoints using hierarchical testing based on a fixed-sequence procedure. If statistical significance is declared for the primary analysis, formal statistical inference will continue at the 0.05 level for the secondary endpoints in the defined sequence until a non-significant result is reached. All other P values from key secondary endpoints, after a non-significant P value is reached, as well as other additional endpoints, will be considered exploratory.

An analysis of covariance (ANCOVA) model with treatment group as fixed effect and baseline value of the endpoint (when applicable) as covariates will be performed for the primary and key secondary continuous endpoints.

Sensitivity analyses will be conducted to estimate sensitivity estimators and to assess the robustness of efficacy results.

Additional Endpoints:

Additional endpoints and subgroup analyses will also be tested at a 2-sided 0.05 significance level.

The analysis of all continuous and categorical additional endpoints will be performed using an ANCOVA model

Safety Analysis:

Safety variables include physical examination, vital signs assessments (heart rate, respiratory rate, sitting blood pressure, and temperature), clinical laboratory assessments (hematology, chemistry, urinalysis), HbA1c, morning serum cortisol, [REDACTED] 12-lead electrocardiogram (ECG), knee radiographs, concomitant medications/therapies, AEs, and signs and symptoms of adrenal insufficiency. Medical history and AEs will be coded using the Medical Dictionary for Regulatory Activities (MedDRA), and concomitant medication will be coded using the World Health Organization Drug (WHODrug) Global Dictionary. Continuous safety data will be summarized by visit and include changes from baseline. Continuous data will also be converted to categorical values where possible (i.e., below, within, and above normal ranges) and summarized in shift from baseline tables. Categorical safety data collected by visit will be summarized showing the counts and percentages in each category at each visit, as well as shifts from baseline as appropriate.

Interim Analysis:

An interim analysis will not be performed.

SAMPLE SIZE DETERMINATION

This is a 3-arm parallel-group randomized controlled study. Approximately 500 patients will be randomized in

According to these assumptions, 500 patients will be randomly assigned in a 2:1:1 ratio to ensure that the study is well powered for primary and key secondary endpoints to be tested via the fixed-sequence testing method.

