- n A diary will be used daily to collect responses from patients on index knee pain over the previous 24 hours. Training regarding entering data into the diary will be given. Patients will first be asked to score their average pain in each knee by NRS over the previous 24 hours at the initial Screening visit. After the first Screening visit (Visit 1), the diary must be completed for each knee in the evening daily for at least 5 of the last 7 days of the screening period before returning to the study site for Visit 2 (Day 1/Baseline). After randomization, the patient will record their response on index knee pain in the diary every evening throughout the study until the last day prior to the EOS/ET visit. Sites should monitor patient compliance of diary entries regularly throughout the 52 weeks. If a patient is not compliant, the site should contact the patient as soon as non-compliance is observed.
- o Procedures for those receiving Injection 2. The patient should be checked for the criteria listed in Section 6.6.3 before study drug administration.
- p Initial rescue medication bottle will be dispensed at Screening and as needed. Between Screening and EOS/ET, patients will record the previous 24-hour use of acetaminophen rescue medication daily into the diary. Rescue medication will be reviewed at every study visit.

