11.3.1.3. Demographics and Other Baseline Characteristics

These analyses will be conducted for all analysis populations.

Demographic variables will include age, sex, race, weight, BMI, and region. Baseline patient characteristics will include medical history, including confirmation of OA diagnosis and time since diagnosis, Kellgren-Lawrence Grade, normalized WOMAC scores, and average daily pain.

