11.3.3.1. Primary Analysis

The primary efficacy analysis and estimation of the primary estimand will be based on the FAS population, the mPP population, and the PP population.

The primary estimand is the difference in mean change from Baseline in WOMAC Pain score at Week 12 between TLC599 vs. Placebo (as defined in the Treatment Assignment Table in Section 7.2). The endpoint and intercurrent events for the primary estimand are defined as follows:

- Endpoint: Change from Baseline in WOMAC Pain score at Week 12
- Intercurrent Events:

An ANCOVA will be performed with treatment group as a fixed effect and Baseline WOMAC Pain score as a covariate. Multiple imputation will be used to impute missing intermittent and post-withdrawal WOMAC Pain scores considered to be missing at random. Post-withdrawal missing data due to lack of efficacy, AE, or surgical procedure/IA drug administration in the index knee will be assumed to be MNAR; all other missing and post-withdrawal data will be assumed to be MAR.

The ANCOVA model will be conducted on each imputation and the results will be combined using Rubin's rules in SAS PROC MIANALYZE.

The least-squares mean comparing TLC599 to Placebo along with the corresponding 95% confidence interval, will be used to estimate the treatment difference.

Sensitivity analyses will be conducted to estimate sensitivity estimators and to assess the robustness of efficacy results, including:

- A sensitivity analysis using a tipping point procedure to assess the robustness of the multiple imputation results.
- A mixed-effects model repeated measures (MMRM) approach will be used as a sensitivity analysis for the primary endpoint. Treatment group, study visit (as a categorical variable) and

site will be modeled as fixed effects, with a treatment-by-visit interaction and baseline WOMAC Pain score as a covariate. Patient will be included as a random effect. Prior to implementing the model, MNAR data due to intercurrent events will be imputed using BOCF and non-missing data affected by the use of intercurrent medications and procedures will be replaced using BOCF, as described for the primary analysis method. The MMRM will include both observed and BOCF imputed data.

If further sensitivity analysis on the primary endpoint is performed, it will be described in the SAP. Descriptive summaries (such as mean, standard error, first quartile, median, third quartile, minimum, and maximum) will also be provided for the primary endpoint.

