11.3.3.2. Secondary Analyses

Continuous secondary endpoints will be analyzed using the same methodology as for the primary endpoint, unless otherwise indicated.

For analysis of categorical secondary endpoints, the difference in the predictive marginal proportions will be the basis of comparison between treatment groups.

The corresponding 95% CI and P value will also be presented.

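### Key secondary endpoint 7 (rescue acetaminophen through Week 12) has no stated pre-randomisation acetaminophen covariate, although the screening diary already records that use

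*Combined protocol and SAP*

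**What the plan says.** Endpoint 7 in Section 11.1.1.2 compares total rescue acetaminophen through Week 12 between Groups A and C. It is a post-dose total, not a change from baseline.

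The plan has two covariate rules that could govern it.

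- Protocol Summary, Efficacy Analysis: the ANCOVA for primary and key secondary continuous endpoints has "treatment group as fixed effect and baseline value of the endpoint (when applicable) as covariates".
- Section 11.3.3.2: "Continuous secondary endpoints will be analyzed using the same methodology as for the primary endpoint, unless otherwise indicated". The primary method in Section 11.3.3.1 reads: "An ANCOVA will be performed with treatment group as a fixed effect and Baseline WOMAC Pain score as a covariate".

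On data collection, the Protocol Summary states: "During the screening period, patients will complete daily diaries including assessments of pain in each knee by NRS as well as rescue medication use". Footnote p of the Schedule of Events (Section 1.1) adds: "Between Screening and EOS/ET, patients will record the previous 24-hour use of acetaminophen rescue medication daily into the diary". Section 8.3.1 (items 16 and 18) has rescue medication dispensed and its use recorded from Screening. Section 8.3.2 has the diary reviewed before randomisation.

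Section 11.3.1.3 lists "normalized WOMAC scores, and average daily pain" among the baseline characteristics; rescue use is not in the list. Section 11.1.2 describes average daily pain relative to the Injection 1 Baseline, but describes weekly acetaminophen only as totals and daily averages, with no baseline.

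**The concern.** A 12-week total has no baseline value in the ordinary sense, so the Summary rule may leave endpoint 7 with treatment alone. The Section 11.3.3.2 route brings in WOMAC Pain, which is a different variable. Neither route clearly reaches the patient's own acetaminophen use before randomisation. That is the obvious candidate predictor of later use, and it has already been recorded. Section 7.10 prohibits NSAIDs from 14 days before Baseline and throughout the study, so the last 7 screening days fall under broadly the same analgesic conditions as follow-up.

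Endpoint 7 also has a position in the fixed sequence of Section 11.3.3. If it misses, endpoints 8 to 12 become exploratory, including endpoint 11, the only key secondary comparison with DSP. Stable between-patient differences in analgesic use that the model leaves unexplained widen the standard error of this test. An unstated covariate also leaves a modelling choice open in a confirmatory test.

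**Working it through.** **Plan's own figure.** Section 11.4 gives about 500 patients at 2:1:1, so A = 500 × 2/4 = 250 and B = C = 500 × 1/4 = 125. The assumptions behind 500 are not visible, so the total cannot be reproduced. That gap is not counted against the plan.

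**Inputs.** From the documents: 250 vs 125 for A vs C, two-sided alpha 0.05. Assumed: 80% unadjusted power (90% as a check), and r, the correlation of screening use with the Week 12 total, from 0.1 to 0.7.

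**Step 1. Effect that gives 80% power unadjusted.** d = (1.960 + 0.842) × √(1/125 + 1/250) = 2.802 × 0.1095 = 0.307 SD. For 90% power, d = 0.355.

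**Step 2. Adjust for screening use.** The variance is multiplied by 1 − r² and the SE by √(1 − r²). Power = Φ(2.802/√(1 − r²) − 1.960).

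| r (assumed) | Variance factor | SE reduction | Power from 80% | Power from 90% |
|---|---|---|---|---|
| 0.1 | 0.99 | 0.5% | 80.4% | 90.3% |
| 0.3 | 0.91 | 4.6% | 83.6% | 92.5% |
| 0.5 | 0.75 | 13.4% | 89.9% | 96.3% |
| 0.7 | 0.51 | 28.6% | 97.5% | 99.5% |

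Example at r = 0.5: 2.802/0.866 = 3.235; 3.235 − 1.960 = 1.275; Φ(1.275) = 0.899.

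**Step 3. Comparator with WOMAC Pain already in the model.** Let w be the correlation of WOMAC Pain with the endpoint and c its correlation with screening use, each assumed at 0.1 or 0.3. Then R² = (r² + w² − 2rwc)/(1 − c²), and the remaining variance ratio is (1 − R²)/(1 − w²). Example at r = 0.5, w = c = 0.3: R² = (0.25 + 0.09 − 0.09)/0.91 = 0.275, so the ratio is 0.725/0.91 = 0.797 and power is 88.1%. Here the 80% starting point belongs to the WOMAC-adjusted model.

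| r | Power range over w and c |
|---|---|
| 0.3 | 82.1% to 83.4% |
| 0.5 | 88.1% to 89.7% |
| 0.7 | 96.5% to 97.7% |

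**Step 4. Cost if the covariate is useless.** With N = 250 + 125 = 375, the variance factor is about 1 + 1/(375 − 4) = 1.0027. Power moves from 80.0% to 79.9%.

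**The case against.** A reader might infer that the plan permits only a same-endpoint baseline and so excludes screening acetaminophen. The text does not say that. The applicability qualifier in the Summary can be read to cover diary use before randomisation, Section 11.3.3.2 allows exceptions, and Section 11.3 leaves detail to a SAP. Parts of the statistical text are also blacked out, so endpoint-specific wording may have been removed. The list in Section 11.3.1.3 need not be exhaustive. What stands is narrower: the visible text does not name the covariate. The contrast between average daily pain and rescue use in Sections 11.1.2 and 11.3.1.3 makes an intended but unstated acetaminophen baseline less likely, without ruling it out.

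The size of the gain is open to challenge. No document gives r or the starting power, and at r = 0.1 almost nothing is gained. Two features could lower r. Section 7.2 says the index knee is identified only at Baseline, whereas on-study rescue is for index-knee pain (Section 8.4.1.5). The 7-day window also includes the 24 hours before Baseline, when acetaminophen is not allowed (Section 7.10).

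Completeness of the screening rescue record is not assured either. The Summary says "The diary must be completed for at least 5 of the last 7 days of the screening period", but inclusion criterion 7, Schedule footnote n and Section 8.3.1 item 17 attach that minimum to pain scoring. Section 8.3.1 item 18 and footnote p set no minimum for rescue entries.

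These points reduce the certainty and size of the benefit, and they show that the covariate needs a careful definition. None shows harm from adjusting.

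**Conclusion.** The point holds as an efficiency recommendation. As written, endpoint 7 is analysed with treatment alone or with treatment plus Baseline WOMAC Pain, depending on which section governs, and available pre-randomisation acetaminophen data are not named in either model.

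The gain is negligible at r = 0.1 and becomes material from about r = 0.3 to 0.5. At those two values power is 83.6% and 89.9% from an assumed 80%, or about 82% to 83% and 88% to 90% if WOMAC Pain is already in the model. All of these figures rest on an assumed r, an assumed starting power and, for the second pair, assumed WOMAC correlations of 0.1 to 0.3.

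A reader might go further and conclude that the planned test is biased or its type I error inflated. It is not: omitting a prognostic covariate from a randomised comparison costs power only. Nor is every trial outcome affected, because endpoint 7 is formally tested only after the primary and six earlier secondary endpoints have succeeded.

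**What to change.** Before unblinding, make these changes for endpoint 7 and the weekly acetaminophen endpoints of Section 11.1.2:

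1. Reconcile the covariate rule in the Protocol Summary with Sections 11.3.3.1 and 11.3.3.2, and state the model for endpoints that are not changes from baseline.
2. Pre-specify mean daily acetaminophen (mg/day) over the last 7 screening days, averaged over completed rescue-diary days, as an ANCOVA covariate. Add it to Baseline WOMAC Pain if that is kept. A daily mean over a fixed window is needed because screening length varies up to 4 weeks.
3. State a rule for patients with no or few rescue entries in that window.
4. Use the same variable as a predictor in the imputation model.
5. Tabulate it with the baseline characteristics in Section 11.3.1.3.

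The cost is a few lines in the SAP and a short derivation. No new data are needed. If the covariate proves unrelated to the endpoint, the loss is one degree of freedom, about 0.1 power point.
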